Aim #1: To determine the effects of CBD on cardiac function in 30 children with DS and LGS. This is the primary aim of the study: The effects of CBD on the cardiac function of 30 children with DS or LGS will be assessed using a 12-lead electrocardiogram (EKG), an optional signal average EKG, and a 24-hour Holter monitor. We hypothesize that there will be no alterations in ventricular repolarization and heart rate variability on the EKGs and Holter monitoring, respectively, after taking CBD for 4-8 weeks, compared to when participants were not taking CBD. *Milestone: Records from 12-lead EKG and 24-hour Holter monitor in 30 patients.*

Note: The following aims are secondary to the primary outcome and goal of assessing the effects of CBD on cardiac function.

Aim #2: To assess signs and symptoms of dysautonomia in the presence and absence of CBD. Signs and symptoms of dysautonomia include parental perception of body temperature, skin color in hands and feet, sweating, pupil size, flushing, feeding issues, heart rate, and constipation. These signs and symptoms will be collected using a previously-established dysautonomia survey. We hypothesize there will be no change in qualitative assessments of signs and symptoms of dysautonomia after taking CBD for 4-8 weeks, compared to when participants were not taking CBD. *Milestone: Completed dysautonomia surveys in 30 patients before and after CBD administration.*

Aim #3: To determine the effects of CBD on the occurrence of seizures. The number of seizures in children who obtain CBD will be assessed using a 7-day seizure diary (Seizure tracker). Caregivers will record the number of

seizures for a 7-day period prior to CBD administration, and repeat the seizure tracking after having received CBD for 4-8 weeks. Change in seizure numbers will be compared pre- and post-CBD administration. We hypothesize that study participants will have lower seizure counts after being on CBD compared to when weren't taking CBD. *Milestone: Completed 7-day seizure diaries in 30 patients before and after CBD administration.*

Study Design and Methodology

[figure not shown]

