Study Design: Thirty patients with DS or LGS who are going to register to take medical cannabis (cannabidiol, or CBD) in the state of Minnesota will be offered the opportunity to participate in this study. If consent is obtained, the patient or guardian will be asked to complete a questionnaire developed for this study that documents observable signs and symptoms of dysautonomia, and to complete a seizure diary for 7 days prior to initially receiving the CBD. Each participant will also have a 12-lead electrocardiogram (EKG), an optional signal average EKG, and wear a 24-hour Holter monitor, all non-invasive measures of cardiac function, prior to being administered the CBD. The EKGs and 24-hour Holter monitor will be interpreted by a cardiac electrophysiologist and will be reviewed for heart rate variability parameters. The dysautonomia questionnaire, seizure diary and cardiac measurements will be repeated 4-8 weeks after the subject has been on a stable regimen of CBD. This time-frame is based on availability of subjects schedules and clinic visits, and it is also greater than 5 half-lives previously reported for CBD (apparent half-life, 21 hours, (15)). Steady-state levels are achieved after 5 half-lives of drug dosing, thus we expect to be at steady-state concentrations.

Subjects who are already on a stable regimen of CBD, yet plan to stop taking CBD at some point for some reason, are also eligible to participate. The patient or guardian will complete the dysautonomia questionnaire and seizure diary (and research staff will be available to help with questions), and the patient will have the 12-lead EKG, an optional signal average EKG, and 24-hour Holter monitor while still on the CBD. The subjects will then come back 4-8 weeks after their last dose of CBD to have these assessments repeated while off of the CBD. Again, this time frame is based on availability of subjects schedules and clinic visits as well as being substantially greater than 5 half-lives of CBD, the standard wash-out period for pharmacological studies.

Sample Size: A power analysis was not used to determine sample size. Current sample size expectations will be 40 subjects based on the number of patients who enroll in the Minnesota state registry and who are also patients at Gillette. This available sample size will allow us to account for potential participant dropout or incomplete data so that we can achieve our target of 30

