patients. This is a pilot study with a limited number of participants, and data collected will be used in a subsequent power analysis to determine the number of subjects needed in a larger study to determine statistical significance. This will be the first study of medical cannabis' effects on autonomic function in children with severe seizures, and due to the anticipated small sample size, these findings will primarily be used as pilot data to guide further characterization of CBD effects on autonomic parameters.

Methodologies: The 12-lead EKG will be used to collect information on rhythm, a detailed assessment of heart rate (RR interval), PR interval, QRS duration, QT and QTc interval, and ST segment changes in order to detect cardiac arrhythmias and other abnormalities (see graphic below). The signal average EKG will take this same information and average them during a 20 minute time period, provided our subject is able to lie still for that amount of time.

Heart rate variability (HRV) will be assessed using the 24-hour Holter ECG recordings. Both time-domain parameters (RR interval [heart rate], SDNN [standard deviation of RR intervals] and SDNN-I [the mean of standard deviation of all RR intervals for all 5 minute segments]) and frequency-domain parameters (VLF [total spectral power of all NN intervals between 0.003 and 0.04Hz], HF [total spectral power of all NN intervals between 0.15 and 0.4Hz] and LF [total spectral power of all NN intervals between 0.04 and 0.15 Hz] amplitude) will be obtained. HRV is a measure of sympathetic/parasympathetic cardiac autonomic balance, with lower HRV parameters indicating increased adrenergic tone.

Data Analysis: The number of participants (30 subjects) is small due to the limited number of patients available for enrollment into this specialized study. The study is an observational study with a cross-over design, where the patients will serve as their own controls. Primary assessments will include determination of any changes in EKG parameters and Holter heart rate variability parameters

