pre- and post-treatment with CBD, as well as the percentage of items in the dysautonomia survey that changed and the number of seizures that occurred pre- and post-treatment with CBD. Appropriate data assessments will be performed to determine whether parametric or nonparametric analyses are the proper approach. Due to the small sample size and potentially highly variable or skewed data due to the complex patient population under investigation, we plan to normalize Holter heart rate variability parameters and EKG parameters and calculate change from “baseline” (off – CBD) to those collected while CBD is being administered at steady-state levels.

We also will compare reported seizure data collected from subjects who enrolled in the study prior to initiation of CBD to those who were already on CBD and then discontinued CBD use to determine if substantial differences are apparent in the two groups, since parent report may be biased. We will also confirm that EKG and Holter monitor data 4-8 weeks post-CBD (from patients who were on CBD but subsequently discontinued use) are not significantly different from baseline data acquired from patients with no previous CBD use, prior to combining all “off – CBD” as baseline values.

Study Participation

The Principal Investigator or research team members will identify subjects who have registered or plan to register with the State of Minnesota to take medical cannabis. Each participant will be in the study for approximately 2 months, and will need to visit Gillette twice. If subjects have not been on CBD, they will make one visit one week prior to starting CBD treatment and one visit after having been on CBD for 4-8 weeks. For subjects that are already on a stable regimen of CBD, yet plan to stop taking CBD at some point, their participation will last 4-8 weeks after their last dose.

Risks and Discomforts

EKG: There is no pain during an EKG; however, the EKG patches may be cold and removing the pads may make the skin red and sore. In some cases, the locations where the EKG patches are placed may need to be shaved.

24-hour Holter monitor: There is no pain during the use of a 24-hour Holter monitor; however, the patches may be cold and removing the pads may make the skin red and sore. In some cases, the locations where the patches are placed may need to be shaved.

Subject Protection

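### The comparison of starters' and stoppers' seizure reports cannot serve its stated purpose as a check on parent-report bias

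*Combined protocol and SAP*

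**What the plan says.** Under Study Design and Methodology, the Study Design paragraph admits two groups. Starters are patients "who are going to register to take medical cannabis (cannabidiol, or CBD) in the state of Minnesota"; they are assessed off CBD and then on it. The second group is described as "Subjects who are already on a stable regimen of CBD, yet plan to stop taking CBD at some point for some reason"; these stoppers are assessed on CBD and then off it. The Data Analysis paragraph adds: "The study is an observational study with a cross-over design, where the patients will serve as their own controls".

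Seizures are counted by caregivers in a 7-day diary in each CBD state (Aim #3). The expected direction is stated: "We hypothesize that study participants will have lower seizure counts after being on CBD".

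Data Analysis then says: "We also will compare reported seizure data collected from subjects who enrolled in the study prior to initiation of CBD" with data from those who discontinued, "to determine if substantial differences are apparent in the two groups, since parent report may be biased". It does not say whether the compared quantity is the off-CBD count, the on-CBD count, the change or a ratio. It does not define a substantial difference, name a test, or say what follows from either result. The next sentence sets a condition for pooling off-CBD values, but only for EKG and Holter data.

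**The concern.** Possible bias in parent report is the reason given for this comparison, and no other safeguard for the seizure diary appears. Staff help with the forms is offered to stoppers' families, but no masked or objective count is described. Families decide to start or stop CBD themselves, so caregivers can be taken to know which state the child is in.

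The bias that matters most in such a diary is expectancy: fewer seizures noticed or recorded while the child is on CBD. It acts in the direction that Aim #3 hypothesises. A check that compares two groups exposed to the same expectancy cannot see the part they share. If agreement were read as reassurance, a change produced wholly by reporting could be presented as an effect of CBD.

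**Working it through.** The plan has no calculation on this point to reproduce, and Sample Size states that no power analysis was used. The question is what the contrast can identify.

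**Set-up.** For the reported on-minus-off change, let θ be the true effect, b the reporting bias tied to being on CBD, and p the drift from first to second diary. Subscript S is starters and T is stoppers. Starters go off then on, and stoppers on then off, so p enters with opposite signs:

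- starters: θ_S + b_S + p
- stoppers: θ_T + b_T − p
- contrast: (θ_S − θ_T) + (b_S − b_T) + 2p

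**Shared bias.** If b_S = b_T, the bias term is 0 whatever its size.

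**Scale.** This cancellation needs a scale on which the bias is constant. Suppose caregivers in both groups record a fraction k of on-CBD seizures, there is no true effect, and the off-CBD mean counts are m_S and m_T. The count changes are (k − 1)m_S and (k − 1)m_T, and they differ by (k − 1)(m_S − m_T), which is not 0 when severity differs. The on/off ratios are both k, so on the ratio scale the bias cancels fully.

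**Illustration.** Assumptions, none from the plan: normal changes with SD 1, shifts of 0.7 SD, no drift unless stated, two-sided t-test at 0.05, 20,000 simulated trials per case, 30 patients (the plan's target) split 15:15 or 25:5.

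| Case | Contrast (SD) | Flagged, 15:15 | Flagged, 25:5 |
|---|---|---|---|
| No effect, shared on-CBD bias −0.7 | −0.7 − (−0.7) = 0 | 5.0% | 4.9% |
| No effect, bias −0.7 in starters only | −0.7 − 0 = −0.7 | 45.5% | 27.9% |
| No bias, true effect −0.7 in starters only | −0.7 − 0 = −0.7 | 45.4% | 27.9% |
| Bias −0.7 in starters, true effect −0.7 in stoppers | (0 + 0.7) + (−0.7 − 0) = 0 | 4.9% | 5.1% |
| No effect, shared drift −0.7 | 2 × (−0.7) = −1.4 | 95.9% | 78.7% |

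In the first row the pooled on-minus-off change is −0.7 SD and is significant in 96% of trials at either split, although CBD does nothing. Rows two and three have different causes and the same contrast and flag rate. Row four shows that bias and selection can offset each other. Row five shows that a drift shared by both groups is visible, because the order is reversed.

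**If levels are compared.** Were off-CBD or on-CBD counts compared instead of changes, any difference in severity between the self-selected groups would enter directly.

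**Power, illustrative only.** The approximate difference detectable with 80% power is (1.960 + 0.842) × √(1/n₁ + 1/n₂). This gives 1.02 SD at 15:15, 1.09 at 20:10 and 1.28 at 24:6. The exact noncentral-t values (28 df) are 1.06, 1.12 and 1.32 SD. Exact power for a 0.5 SD difference is 26%, 24% and 18%. The plan gives neither the split nor a test for this comparison.

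**The case against.** The strongest reply is that the plan never draws the inference at issue. It says it will look for substantial differences and acknowledges that parent report may be biased; it does not say that agreement shows the absence of bias. It can be read as a descriptive look at heterogeneity prompted by an admitted weakness. That stands in part: the documents contain no invalid conclusion, only a check whose stated reason it cannot meet.

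Three stronger readings are tempting, and the documents do not support them:

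- **That agreement would license pooling the seizure data.** The only pooling condition concerns EKG and Holter values. Nothing of the kind is attached to the seizure comparison.
- **That neither result carries any information about bias, or that a common bias always gives a difference of exactly zero.** Drift shared by both groups enters the contrast doubled, unshared bias also enters it, and proportional under-reporting does not cancel in count differences when severity differs. The comparison is confounded rather than empty, and a marked difference is a fair reason for caution.
- **That a difference would probably mean stoppers had not benefited.** The plan leaves the reason for stopping open, so selection is a possible cause and no more can be said.

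It is also fair that the power figures do not carry the argument. The plan calls itself a pilot without a power analysis, and a larger sample would not cure a problem of identification.

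**Conclusion.** The concern holds in this form: the starter-stopper comparison cannot do what it is included to do. Agreement cannot exclude reporting bias tied to CBD state and similar in both groups, and a difference cannot be attributed to bias as opposed to self-selection or diary drift. This follows from the structure of the contrast and does not depend on any assumed SD, split or test. It does assume that caregivers know the CBD state, which the design implies, and full cancellation assumes a scale on which the bias is constant. The 5% and 96% figures rest on the assumed 0.7 SD bias and show how far the check and the pooled result can diverge.

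The reach is limited. The aims section makes seizures secondary to the cardiac aim, although Data Analysis lists seizure counts among the primary assessments. The change is worth making because the comparison is the only protection offered for Aim #3.

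**What to change.** In Data Analysis:

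1. Describe the comparison as a check of heterogeneity and of order or drift between starters and stoppers, not of parent-report bias.
2. Name the compared quantity as the within-patient on/off seizure ratio, and report it with a 95% CI separately for starters and stoppers. State in advance how a diary week with no seizures is handled, since a ratio with a zero off-CBD count is undefined.
3. Record each stopper's reason for stopping and show it beside the group results.
4. State that agreement between groups does not exclude a shared on-CBD reporting bias, and that a difference may reflect unshared bias, self-selection or drift.
5. Word the Aim #3 conclusion as an unmasked, caregiver-reported change.

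The cost is a few sentences and one recorded item, with no added patients or visits. The downside is a slightly weaker Aim #3 claim. Reporting the groups separately without items 1 and 4 would leave the comparison labelled as a bias check.

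### A non-significant comparison of off-CBD levels between different children cannot justify combining stoppers with starters, and it tests levels when the outcome is within-child change

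*Combined protocol and SAP*

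**What the plan says.** All references are to the combined protocol and SAP, under Study Design and Methodology.

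- **Two routes in (Study Design).** Most children are measured before CBD and again on it (starters). The second route is for "Subjects who are already on a stable regimen of CBD, yet plan to stop taking CBD at some point for some reason"; they are measured on CBD and again 4-8 weeks after the last dose (stoppers). Families choose the order; it is not randomised.
- **Outcome (Data Analysis).** "Primary assessments will include determination of any changes in EKG parameters and Holter heart rate variability parameters" The design is one "where the patients will serve as their own controls", and change is calculated from the off-CBD value "to those collected while CBD is being administered at steady-state levels".
- **The check (Data Analysis).** Before the off-CBD values are combined, the team is to confirm that stoppers' off-CBD EKG and Holter data "are not significantly different from baseline data acquired from patients with no previous CBD use". No margin, test level, group sizes or action on failure are given.
- **Other group comparison (Data Analysis).** One starter-versus-stopper comparison is planned: "compare reported seizure data collected from subjects who enrolled in the study prior to initiation of CBD to those who were already on CBD". It covers seizures only.
- **Size and use (Sample Size).** The target is 30 children, with no power analysis. "Current sample size expectations will be 40 subjects based on the number of patients who enroll in the Minnesota state registry" who are also patients at the site. The "data collected will be used in a subsequent power analysis to determine the number of subjects needed in a larger study".

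**The concern.** There are two separate faults.

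First, the natural purpose of the check is to show that stopping CBD returns a child's values to an untreated state. Absence of significance shows that only if the test would probably have detected a difference that matters. With so few children a pass is the likely result whether or not the groups agree.

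Second, the check compares off-CBD levels between different children, while the analysis uses each child's own change. Equal off-CBD levels are neither necessary nor sufficient for the raw changes to agree. The groups may differ in level for reasons that cancel within a child, or share a level and change by different amounts.

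A pass would be read as support for one common baseline. Stoppers are self-selected and the order is not randomised, so the pooled change could be off in either direction with little chance that the check shows it. That pooled change is meant to inform the size of a larger study.

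**Working it through.** **Inputs.** From the documents: 30 children targeted, 40 expected. The documents give no split, SD, test level or margin, so there is no figure of the plan's to reproduce. Assumed: a two-sided 5% two-sample t-test, equal SDs, and differences in units of the between-child SD of off-CBD values. Splits are starters/stoppers: 15/15, 20/10, 25/5 and 27/3 for 30 children; 20/20 is the best case if all 40 complete.

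**Step 1: what the level check can detect.** The standard error of the difference is SE = √(1/n₁ + 1/n₂). Power comes from the noncentral t with n₁ + n₂ − 2 degrees of freedom and noncentrality d/SE. The 95% CI half-width is t(0.975) × SE. At 20/10, SE = √(1/20 + 1/10) = 0.387, the noncentrality for 0.5 SD is 0.5/0.387 = 1.29, and the half-width is 2.048 × 0.387 = 0.79.

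| Split | Power, 0.5 SD | Detectable at 80% power | 95% CI half-width |
|---|---|---|---|
| 15/15 | 26% | 1.06 SD | 0.75 SD |
| 20/10 | 24% | 1.12 SD | 0.79 SD |
| 25/5 | 17% | 1.42 SD | 1.00 SD |
| 27/3 | 12% | 1.77 SD | 1.25 SD |
| 20/20 | 34% | 0.91 SD | 0.64 SD |

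An equal split maximises power for a given total, so 26% and 34% are ceilings. A true half-SD mismatch therefore passes at least 100 − 34 = 66% of the time.

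**Step 2: faults the check might be expected to catch.** Let δ be the true on-minus-off change.

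- *Incomplete return.* If an amount c of the effect persists after stopping, stoppers' off-CBD level shifts by c and their change becomes δ − c. Take δ = 0.30 SD. With c = 0.15 SD the check is significant in 7%, 7% and 6% of trials at 15/15, 20/10 and 25/5. With c = 0.30 SD (stoppers' change is zero) it is significant in about 12%, 12% and 9%. In that second case the pooled change is 0.30 × n₁/(n₁ + n₂) = 0.15, 0.20 and 0.25 SD instead of 0.30.
- *Period effect.* Starters are off CBD at the first visit and stoppers at the second. A visit shift of p = 0.3 SD moves the off-CBD contrast by 0.3 SD and is flagged in the same 12%, 12% and 9%. Starters' change becomes δ + p and stoppers' becomes δ − p, so the pooled change is off by p(n₁ − n₂)/(n₁ + n₂) = 0, 0.10 and 0.20 SD.

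**Step 3: level against change.** Simulation (60,000 runs, within-child correlation 0.8, true change 0.30 SD) at 15/15, 20/10 and 25/5:

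- A 0.8 SD level difference with identical raw changes fails the check in 56%, 51% and 35% of trials, although the pooled raw change is correct at 0.30.
- A group difference confined to on-CBD values is flagged in about 5%, the false-alarm rate.

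**Step 4: many parameters.** The Methodologies paragraph lists 5 continuous EKG parameters (RR, PR, QRS, QT, QTc) and 6 Holter parameters (RR, SDNN, SDNN-I, VLF, LF, HF). If the groups were identical and the 11 tests independent, at least one would be significant with probability 1 − 0.95¹¹ = 43%; positive correlation lowers this. The plan does not say what follows if some parameters differ.

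**The case against.** The best defence has four parts.

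- **Washout.** The Study Design paragraph cites a 21-hour half-life. Five half-lives are 5 × 21/24 = 4.4 days, and the shortest off-CBD interval is 28 days, or 28 × 24/21 = 32 half-lives. The check therefore supplements a pharmacological argument, and the persistence scenarios above are not what the plan expects. This stands for residual drug. It does not address lasting physiological change, self-selection or period effects.
- **Little rests on the check.** Every child has an own off-CBD value, a stable level cancels in raw paired differences, and this is a declared pilot with no confirmatory claim. This also stands, and it limits the harm. Pilot status excuses low power, but not reading a weak null result as agreement.
- **Level is the right quantity for pooling a baseline.** For merging off-CBD values as such, that is fair. The plan also intends to normalise the parameters by an unstated method; if that uses the off-CBD level, level differences could enter the change score, so Step 3 applies to raw change only. The low power in Step 1 applies either way.
- **Few stoppers may enrol.** The check then matters less, but it is also at its weakest (12% power at 27/3).

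It can also be said that stoppers who simply respond differently make the pooled value an average over a mixed group, which is not an error caused by the check. That is right, and such heterogeneity is not counted here as part of its size.

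**Conclusion.** The concern holds and should be fixed. As written, the plan treats a non-significant between-child comparison as confirmation of agreement. With 30 children it has at most 26% power for a 0.5 SD difference (34% with 40), and even in the best case a true difference must reach about 0.9 SD to be found with 80% power. It is also aimed at levels when the outcome is within-child change, and no starter-versus-stopper comparison of cardiac change is planned.

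The figures rest on an assumed 5% two-sided t-test, equal SDs and assumed splits. The power ceilings do not depend on the split. The size of any bias in the pooled change is unknown; the values in Step 2 are illustrations. The check itself need not bias a raw paired estimate, so the damage is mainly to interpretation and to planning the larger study.

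**What to change.** Delete the significance condition and replace it with text such as:

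> For each EKG and Holter parameter we will compute each child's own on-minus-off difference on one scale fixed before the data are seen (for example raw for EKG intervals, RR, SDNN and SDNN-I; log for VLF, LF and HF). We will report the mean change with 95% CI for starters and stoppers separately, and the between-group difference in change with 95% CI. The pooled paired change will be given as a summary, labelled as mixing two non-randomised orders. The difference in off-CBD level between stoppers and children with no previous CBD use will be reported with 95% CI as description only; no p-value decides whether groups are combined. The by-group estimates, not only the pooled one, will be considered when sizing the larger study.

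The cost is a few sentences; no new data, visits or patients are needed. The change makes group differences visible and yields a starter-only estimate. It does not remove selection or period effects from the pooled value.

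The intervals will be wide. With SD of change √(2(1 − ρ)), the 95% half-widths in SD units are:

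| Estimate | ρ = 0.8 | ρ = 0.5 |
|---|---|---|
| Pooled, 30 children | 0.24 | 0.37 |
| 20 starters | 0.30 | 0.47 |
| 10 stoppers | 0.45 | 0.72 |
| 5 stoppers | 0.79 | 1.24 |
| Contrast in change, 20/10 | 0.50 | 0.79 |

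At 20/10 the contrast has 22% power for a 0.3 SD difference if ρ = 0.8 and 12% if ρ = 0.5. At ρ = 0.5 it is no more precise than the level check. The gain is the right quantity and an honest interval, so the contrast must not become a new condition for pooling. An equivalence test is not a practical substitute: with an assumed margin of 0.5 SD and no true difference, 80% power needs about 2 × ((1.645 + 1.282)/0.5)² ≈ 69 children per group.

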contributor to mortality (5, 6). It has been reported that children with DS exhibited a significantly higher number of signs and symptoms of autonomic nervous system abnormalities than children in a control group (7). Studies of electrical and autonomic cardiac function in patients with DS demonstrated an imbalance of cardiac autonomic function toward a relative predominance of adrenergic tone compared to both healthy children and patients with other forms of epilepsy, and this finding was independent of the use of antiepileptic medications (8, 9). This suggests that dysfunction in the autonomic nervous system, or dysautonomia, is a significant factor in this condition. A number of these patients have seizures triggered by autonomic stimulation (e.g., strong emotion), and many have pronounced autonomic features (e.g., flushing of face, pallor or tachycardia) during ictal events. Modulating autonomic nervous system tone may potentially affect seizure control and risk for SUDEP.

Investigators have been unable to accurately determine the incidence of SUDEP in patients with LGS, perhaps due to variation in the etiology and definition of LGS. In addition, the literature available on LGS and autonomic nervous system dysfunction is sparse, as is the literature on LGS and cardiac function. Patients with LGS may be at an increased risk for cardiac abnormalities (10). Nei (2012) documented sinus-tachycardia, T wave inversion and ST segment depression during tonic seizures, as well as 3 to 4.8 seconds of asystole during sleep in subjects wearing a subcutaneously implanted loop recorder (10). Studies of SUDEP have identified increased risk in those with early onset and medically intractable epilepsy, neurologic abnormalities, and a need for multiple medications. Children with LGS meet all these criteria.

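### The check that decides whether off-CBD cardiac values may be combined compares different, self-selected children without adjustment, so syndrome or age mix can mimic or hide a carry-over effect

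*Combined protocol and SAP*

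**What the plan says.** The Study Design paragraph admits two kinds of participant. Some are about to start CBD and are assessed before it and again on it. Others are already on a stable regimen and "plan to stop taking CBD at some point for some reason, are also eligible to participate"; they are assessed on CBD and again 4-8 weeks after the last dose. Every child therefore contributes one off-CBD assessment and belongs to one entry group.

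The Data Analysis paragraph describes the main analysis as within child. It then adds a check: the off-CBD EKG and Holter data of those who stopped are to be confirmed as values that "are not significantly different from baseline data acquired from patients with no previous CBD use", and this is done "prior to combining all" off-CBD values as baseline. No covariate, stratum or matching factor is named, and neither is a test or significance level. On method the paragraph says only: "Appropriate data assessments will be performed to determine whether parametric or nonparametric analyses are the proper approach". It also plans a normalisation of EKG and Holter parameters. It does not define this, explains it by small numbers and variable or skewed data, and does not tie it to the check.

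The background section says that DS shows a relative "predominance of adrenergic tone compared to both healthy children and patients with other forms of epilepsy". The study enrols DS or LGS. On sample size the protocol states: "A power analysis was not used to determine sample size".

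**The concern.** The within-child design protects the on/off change from fixed differences between children. The check has no such protection, because it sets levels in one group of children against levels in another. Nothing balances the groups: one is about to start CBD, and the other has chosen to stop it for reasons the protocol leaves open.

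The protocol itself gives a reason why levels could differ without any lasting effect of CBD. It links DS to a shift in cardiac autonomic tone and treats lower heart rate variability (HRV) as a sign of increased adrenergic tone. If starters and stoppers differ in DS:LGS mix, the parameters under test may differ too. Age could act in the same way, if these parameters vary with age.

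Two errors are possible. A difference in case mix may be read as carry-over, so that values are kept apart without cause. Or a real carry-over may be cancelled by an opposite difference in case mix, so that values are combined and carry-over is declared absent. More children would not remove this bias.

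**Working it through.** The plan gives no power, SD, margin or significance level for this check, so there is no figure of its own to reproduce. The following is an illustration on stated assumptions.

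**Inputs from the protocol.** Target of 30 children; two disjoint entry groups; mixed DS and LGS; wash-out of 4-8 weeks; CBD half-life of 21 hours.

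**Assumed inputs.** Two-sided 5% test; starter:stopper splits of 15:15, 20:10 and 24:6; DS and LGS differing by 0.8 SD; DS share 50% in starters and 20% in stoppers; entry groups 0.5 SD apart in age; correlation of 0.5 between age and the parameter. The protocol gives none of these.

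**Step 1: spurious difference with no carry-over.**
- Syndrome: (0.50 - 0.20) x 0.8 = 0.24 SD.
- Age: 0.5 x 0.5 = 0.25 SD.
- Same direction: 0.24 + 0.25 = 0.49 SD. Opposite directions: 0.25 - 0.24 = 0.01 SD.

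**Step 2: chance that the unadjusted check flags a difference.** Two-sample t test on 28 degrees of freedom, with noncentrality d x sqrt(n1 n2 / 30). At 15:15 and d = 0.49 this is 0.49 x sqrt(7.5) = 1.34.

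| Spurious difference | 15:15 | 20:10 | 24:6 |
|---|---|---|---|
| 0.01 SD (opposite directions) | 5% | 5% | 5% |
| 0.24 SD (syndrome only) | 10% | 9% | 8% |
| 0.25 SD (age only) | 10% | 10% | 8% |
| 0.49 SD (both, same direction) | 25% | 23% | 18% |

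Varying the age inputs alone (correlation 0.3 to 0.7, age gap 0.5 to 1 SD) gives a bias of 0.15 to 0.70 SD. The false-flag rate is then 6.8-45.7% at 15:15 and 6.6-41.5% at 20:10.

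**Step 3: does adjustment repair it?** A simulation with the Step 1 inputs, both biases in the same direction, gave unadjusted rejection of about 18-27% across the splits. A model with entry group, age and syndrome gave about 5%, with no bias.

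A second, more extreme scenario shows masking. It uses a 20:10 split, age correlation 0.5, age gap 1 SD, a syndrome effect of 0.5 SD and mixes 30 points apart, so the bias is 0.5 x 1 + 0.5 x 0.3 = 0.65 SD. Over 8,000 runs:

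| True carry-over | Unadjusted estimate; rejection | Adjusted estimate; rejection |
|---|---|---|
| 0 | 0.65 SD; 34.6% | 0.00 SD; 5.4% |
| -0.65 SD | 0.00 SD; 5.2% | -0.65 SD; 35.4% |

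Adjustment removes the bias from these two factors. It does not supply power: a true carry-over of 0.65 SD is still missed about two times in three.

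**Step 4: precision without confounding.** The 95% CI half-width for the unadjusted group difference is t(0.975, 28) x sqrt(1/n1 + 1/n2), that is 0.75 SD at 15:15 and 0.79 SD at 20:10. Power for a true 0.5 SD difference is 26% and 24%.

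**The case against.** - **The primary analysis is within child.** This stands. Stable age and syndrome differences cancel from each child's on/off change. A reader might infer that the primary cardiac result is biased by case mix; the design does not support that.
- **The documentary basis is thin.** This stands in part. The background contrasts DS with other forms of epilepsy, not with LGS, and calls the LGS literature on autonomic dysfunction sparse. The text supplied gives no age range and no age dependence of the parameters. A reader might infer that stoppers are older, or include fewer children with DS; prior exposure to CBD implies neither. What remains is that the groups are unbalanced by design and that the protocol ties syndrome to autonomic tone.
- **The plan normalises the parameters.** The term is undefined and is justified by skew and small numbers. Change from baseline cannot be what the check compares, because the off-CBD value is itself the baseline. Age-referenced scores, if intended, would reduce the age part and leave syndrome.
- **Wash-out is ample.** Four weeks is 28 x 24 / 21 = 32 half-lives and eight weeks is 64, so residual drug is unlikely on the protocol's own figure. That does not exclude a lasting effect of another kind, and it does not make the planned check interpretable.
- **It is a pilot, and low power matters more.** Low power is a real and separate limit. But the pilot data are meant to inform a larger study, so whether the off-CBD state is a sound common baseline matters.

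**Conclusion.** The concern holds for the combining decision and for any statement that there is no carry-over. As written, a significant difference could be case mix, and a non-significant one could hide a real effect.

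The size is uncertain and should be given as a range. One factor at 0.24-0.25 SD moves the false-flag rate from 5% to 8-10%. The 18-25% figure needs two assumed biases in the same direction and is not an expected value; opposite biases leave the rate near 5%. The syndrome route has partial support in the protocol, while the age route and all magnitudes are assumptions.

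A reader might also expect adjustment to tighten the interval by the textbook factor sqrt(1 - R²): 13% at R² = 0.25 and 19% at R² = 0.35. That ignores the imbalance of the covariates between groups and the lost degrees of freedom. In simulation the interval ranged from about 16% narrower to 5% wider. The case for adjustment is removal of bias, not precision.

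**What to change.** In the Data Analysis paragraph, replace the unadjusted check with a linear model for each off-CBD EKG and Holter parameter (HRV on the log scale), with terms for entry group (stopped, or not yet started), age and syndrome. Report the adjusted group difference with its 95% CI, and state that non-significance will not be read as proof of no carry-over. Use the same two covariates in the comparison of seizure data between starters and stoppers.

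The cost is a sentence or two of text and two degrees of freedom in about 30 children. Syndrome is known at entry and age should be in the clinic record. The interval may become slightly narrower or slightly wider. Adjustment does not cure low power, and it does not deal with differences tied to the reason for stopping CBD; the report should say so.
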